## 6. ANALYSES AND SUMMARIES

### 6.1. Primary Endpoints

#### 6.1.1. Phase 1b

DLT rate is calculated as the number of DLT-evaluable participants with DLTs in the DLT observation period divided by the number of DLT-evaluable participants in the DLT observation period.

Analyses of DLT will be performed on DLT Evaluable Analysis Set. DLT rate will be summarized and listed by dose levels.

#### 6.1.2. Phase 2

The primary endpoint is ORR, defined as the proportion of participants with an objective response ([Section 3.1.2](#)) per IMWG response criteria as determined by investigator.

ORR will be analyzed in the Safety Analysis Set. The median ORR and its corresponding 2-sided 90% credible interval based on the posterior distribution will be calculated. In addition, the observed point estimate of ORR will be calculated along with the 2-sided 90% CIs using the Clopper-Pearson method (exact CI for a binomial proportion).

The frequency (number and percentage) of participants with BOR by investigator in the following response categories will be summarized:

- sCR; CR; VGPR; PR; MR; SD; PD; Not evaluable (NE);
- Objective response (sCR + CR + VGPR + PR);
- VGPR or better (sCR + CR + VGPR);
- Clinical benefit response (sCR + CR + VGPR + PR + MR).

BOR will be assessed based on reported timepoint responses by investigator recorded at evaluation time points from the date of first dose until disease progression, death or start of new anticancer therapy using IMWG response criteria. BOR needs to be confirmed according to IMWG response criteria (Table 3). If a participant meets multiple criteria in determining confirmed BOR, the order of criteria in this table will be used to define the hierarchy. No minimal time interval is required between the disease assessments, but a different sample is required for confirmation.

**Table 3. Derivation Rules for Confirmed Best Overall Response per IMWG Response Criteria**

Scenario	Timepoint response at:			BOR
	Assessment 1	Assessment 2	Assessment 3	
1	sCR	sCR		sCR
2	sCR	NE	sCR	
3	CR/VGPR/PR/MR/SD	sCR	sCR	
4	CR	sCR/CR		CR
5	sCR/CR	CR		
6	CR	NE	CR	
7	VGPR/PR/MR/SD	CR	CR	
8	VGPR	sCR/CR/VGPR		VGPR
9	sCR/CR/VGPR	VGPR		
10	VGPR	NE	VGPR	
11	PR/MR/SD	VGPR	VGPR	
12	PR	sCR/CR/VGPR/PR		PR
13	sCR/CR/VGPR/PR	PR		
14	PR	NE	PR	
15	MR/SD	PR	PR	
16	MR	sCR/CR/VGPR/PR/MR		MR
17	sCR/CR/VGPR/PR/MR	MR		

090177e196913362\Approved\Approved On: 19-Mar-2021 12:41 (GMT)

Scenario	Timepoint response at:			
	Assessment 1	Assessment 2	Assessment 3	BOR
18	MR	NE	MR	
19	SD	MR	MR	
20	SD	No further assessments		SD a
21	SD	sCR/CR/VGPR/PR/MR/SD/PD	No further assessments	
22	sCR/CR/VGPR/PR/MR	NE/PD or no further assessment	No further assessments	
23	PD (due to reasons other than EMD or bone marrow plasma cells)	PD (any reason) including PD after initiation of new anticancer therapy		PD
24	PD (due to reasons other than EMD, or bone marrow plasma cells)	Participant died due to disease before further disease assessment (including death due to disease under study after initiation of new anticancer therapy)		
25	PD (due to EMD, or bone marrow plasma cells) b	sCR/CR/VGPR/PR/MR/SD/NE/PD or no further assessments	No further assessments	
26	Death (due to disease under study)			
27	Death (not due to disease under study)			NE
28	NE	No further assessment		
29	NE	NE/PD (due to reasons other than EMD or bone marrow plasma cells)	No further assessments	
30	PD (due to reasons other than EMD, or bone marrow plasma cells)	sCR/CR/VGPR/PR/MR/SD/NE	No further assessments	
EMD = extramedullary disease; IMWG = International Myeloma Working Group, sCR = stringent complete response, CR = complete response, PR = partial response, VGPR = very good partial response, SD = stable disease, PD = progressive disease, NE = not evaluable. a SD does not need to be confirmed. b PD due to EMD (includes any new lesion, increased extramedullary or paramedullary lesions/, plasmacytomas), or bone marrow plasma cells does not need to be confirmed.				

090177e196913362\Approved\Approved On: 19-Mar-2021 12:41 (GMT)

## 6.2. Secondary Efficacy Endpoints

### 6.2.1. Cumulative Complete Response Rate

CCRR is defined as the proportion of participants with a CCR per IMWG criteria as determined by investigator.

Point estimates of CCRR will be calculated along with corresponding 2-sided exact 95% CIs using the Clopper-Pearson method.

### 6.2.2. Progression-free Survival

PFS is defined as the time from the date of first dose until PD per IMWG criteria as determined by investigator or death due to any cause, whichever occurs first. PFS will be calculated as follows:

$$\text{PFS (months)} = [\text{date of event or censoring} - \text{date of first dose} + 1] / 30.4375.$$

PFS will be censored as follows:

- For participants who do not have an event (PD per IMWG criteria or death due to any cause), censoring will occur on the date of the last adequate disease assessment;
- For participants who start a new anticancer therapy (as defined in [Section 5.2.6](#)) prior to an event, censoring will occur on the date of the last adequate disease assessment before the new anticancer therapy;
- For participants with an event after a gap of 2 or more missing disease assessments, censoring will occur on the date of the last adequate disease assessment before the gap;
- Participants who do not have an adequate baseline disease assessment or who do not have an adequate post-baseline disease assessment will be censored on the date of first dose of study intervention unless death occurs on or before the time of the second planned disease assessment (ie,  $\leq 8$  weeks after the date of first dose) in which case the death will be considered an event.

The censoring and event date options to be considered for the PFS analysis are presented in [Table 4](#). Adequate baseline disease assessment and adequate post-baseline disease assessment are defined in [Section 5.2.9](#) and [Section 5.2.10](#), respectively.

**Table 4. Outcome and Event Dates for PFS Analyses**

Scenario	Date of Event/Censoring	Outcome
No adequate baseline assessment	Date of first dose of study intervention	Censored a
Progression or death 1. After at most 1 missing or inadequate post-baseline disease assessment or 2. ≤62 days after date of first dose of study intervention	Date of progression or death	Event
Progression or death after 2 or more missing or inadequate disease assessments b	Date of last adequate assessment b documenting no PD prior to new anticancer therapy or missed disease assessments	Censored
No progression or death		
New anticancer therapy given prior to PD or death		

a. If the participant dies ≤62 days (within 2 cycles accounting for 3 day visit window) after date of first dose of study intervention and did not initiate any new anticancer therapy, the death is an event with date on the death date.

b. If there are no adequate post-baseline disease assessments prior to PD or death, then the time without adequate assessment should be measured from the date of first dose of study intervention; if the criteria were met, the censoring will be on the date of first dose of study intervention.

PFS = progression-free survival; PD = progressive disease

Kaplan-Meier estimates (product-limit estimates) will be presented and displayed graphically where appropriate, together with a summary of associated statistics including the median PFS time with 2-sided 95% CIs. The CIs for the median will be calculated according to Brookmeyer and Crowley, 1982.

The PFS rate at 3, 6, 9, 12, 18, and 24 months (and in subsequent 12-month increments while there are participants still at risk) will be estimated with corresponding two-sided 95% CIs. The CIs for the survival function estimates at the timepoints defined above will be derived using the log(-log) method according to Kalbfleisch and Prentice (conftype=loglog default option in SAS Proc LIFETEST). The estimate of the standard error will be computed using Greenwood's formula. Frequency (number and percentage) of participants with each event type (PD or death) and censoring reasons will be presented along with the overall event and censor rates.

Reasons for censoring will be summarized according to the categories in Table 5. If a participant meets multiple definitions for censoring the list will be used to define the hierarchy.

**Table 5. PFS Censoring Reasons and Hierarchy**

Hierarchy	Condition	Censoring Reason
1	No adequate baseline assessment	No adequate baseline assessment
2	Start of new anticancer therapy before event.	Start of new anticancer therapy
3	Event after 2 or more missing or inadequate post-baseline disease assessment after date of first dose	Event after missing or inadequate assessments a
4	No event and [withdrawal of consent date $\geq$ date of first dose or End of study (EOS) = Participant refused further follow-up]	Withdrawal of consent
5	No event and lost to follow-up in any disposition page	Lost to follow-up
6	No event and [EOS present or disposition page for any EPOCH after screening says participant will not continue into any subsequent phase of the study] and no adequate post-baseline disease assessment	No adequate postbaseline disease assessment
7	No event and none of the conditions in the prior hierarchy are met	Ongoing without an event

a. More than 62 days after last adequate disease assessment while on treatment with study intervention; more than 70 days after discontinuing study intervention without PD.

The PFS time or censoring time and the reasons for censoring will also be presented in a data listing.

### 6.2.3. Duration of Response

DOR is defined, for participants with an OR per IMWG criteria as determined by investigator, as the time from the first documentation of OR that is subsequently confirmed, until PD per IMWG criteria, or death due to any cause, whichever occurs first. DOR will be calculated as follows:

$$\text{DOR (months)} = [\text{date of event or censoring} - \text{first date of OR} + 1] / 30.4375$$

The censoring rules for DOR are as described for PFS in [Section 6.2.2](#), except that participants will not be censored for inadequate baseline assessment or for no adequate post-baseline assessment, as only participants with an OR are included in the analysis of DOR.

If at least 3 participants achieve an OR and subsequently have an event, DOR will be estimated using the same Kaplan-Meier method as described for PFS in [Section 6.2.2](#) and displayed graphically where appropriate. Otherwise only listings will be provided.

The DOR rate at 3, 6, 9, and 12 months (and in subsequent 6-month increments while there are participants still at risk) will be estimated with corresponding two-sided 95% CIs.

#### 6.2.4. Duration of Cumulative Complete Response

DOCCR is defined, for participants with a CCR per IMWG criteria as determined by investigator, as the time from the first documentation of CCR that is subsequently confirmed, until PD per IMWG criteria, or death due to any cause, whichever occurs first. DOCCR will be calculated as follows:

$$\text{DOCCR (months)} = [\text{date of event or censoring} - \text{first date of CCR} + 1] / 30.4375$$

The censoring rules for DOCCR are as described for DOR in [Section 6.2.3](#).

If at least 3 participants achieve a CCR and subsequently have an event, DOCCR will be estimated using the same Kaplan-Meier method as described for DOR in [Section 6.2.3](#) and displayed graphically where appropriate. Otherwise only listings will be provided.

The DOCCR rate at 3, 6, 9, and 12 months (and in subsequent 6-month increments while there are participants still at risk) will be estimated with corresponding two-sided 95% CIs.

#### 6.2.5. Overall Survival

OS is defined as the time from the date of first dose until death due to any cause and will be calculated in months as follows:

$$\text{OS (months)} = [\text{date of death or censoring} - \text{date of first dose} + 1] / 30.4375$$

Survival status is expected to be collected irrespective of study intervention discontinuation or participant's request to discontinue study procedures. All participants who have not withdrawn consent for further participation in the study should be followed for survival until the end of the study. OS for participants not known to have died are censored on the date of last known alive.

OS time will be estimated using the same Kaplan-Meier method and displayed graphically as described for PFS in [Section 6.2.2](#). Median OS and 2-sided 95% CI will be provided. The OS rate at 12, 24, and 36 months (and in subsequent 12-month increments while there are participants still at risk) will be estimated with corresponding two-sided 95% CIs.

Frequency (number and percentage) of participants with death events and censoring reasons will be presented along with the overall event and censor rates. The event and censoring reasons are as follows:

- Death;
- Ongoing and no death;
- Withdrawal of consent;
- Lost to follow-up.

The OS time or censoring time and the reasons for censoring will also be presented in a listing.

### 6.2.6. Time to Response

TTR is defined, for participants with an OR per IMWG criteria as determined by investigator, as the time from the date of first dose to the first documentation of OR that is subsequently confirmed. TTR will be calculated in weeks as follows:

$$\text{TTR (weeks)} = [\text{date of first OR} - \text{date of first dose} + 1] / 7$$

TTR will be summarized using simple descriptive statistics (mean, standard deviation, minimum, median, and maximum).

### 6.2.7. Minimal Residual Disease Negativity Rate

MRD negativity rate is defined as the proportion of participants with negative MRD (assessed by central lab) per IMWG sequencing criteria at any time after first dose of study intervention.

Point estimates of MRD negativity rate will be calculated along with the 2-sided 95% CIs using the Clopper-Pearson method.

MRD negativity rate will also be summarized among participants who achieved CCR with 2-sided 95% CIs.

If data permits, MRD-negativity status at 1-year, 2-year and 3-year from the time of first documentation of MRD-negativity may be summarized by number and percentage among participants who achieved CCR and MRD negativity.

## 6.3. Other Secondary Endpoints

### 6.3.1. Pharmacokinetic/Pharmacodynamics

Pharmacokinetic parameter analyses will be based on the PK Analysis Set.

#### 6.3.1.1. PF-06863135

PK data analyses will include descriptive summary statistics of the predose and postdose serum concentrations, and PK parameters of PF-06863135 for each sub-study by study visit and time point. Box and Whisker plots for predose PF-06863135 concentrations by study visit and PK parameters ( $C_{\max}$  and  $AUC_{\text{last}}$ ) will be generated. Values below the limit of quantitation for PF-06863135 and other analytes will be treated as zero in the descriptive statistics calculations. For additional details on handling missing and BLQ values, please refer to [Section 5.3.1](#).

In addition, the PK data from this study may be used to develop a population PK model. PK data from this study maybe pooled with other studies for population PK model development. The correlations between PF-06863135 exposure parameters and pharmacodynamic biomarker, efficacy and/or safety outcomes will be explored if data allows. The results of these modeling analyses will be reported separately from the clinical study report.

### **6.3.1.2. Nirogacestat**

PK data analyses will include descriptive summary statistics of predose serum concentrations of nirogacestat by study visit and time point. Box and Whisker plots for predose serum concentrations of nirogacestat by study visit will be generated. PK data from this study maybe pooled with other studies for population PK model development. The correlations between nirogacestat exposure parameters and pharmacodynamic biomarker, efficacy and/or safety outcomes will be explored if data allows. The results of these modeling analyses will be reported separately from the clinical study report.

### **6.3.2. Immunogenicity**

Immunogenicity data will be analyzed in the Immunogenicity Analysis Set.

The percentage of participants with positive ADA will be summarized. Listings and summary tabulations of the ADA data at baseline and post-baseline will be generated. Samples may also be analyzed for the presence of neutralizing antibodies (NAb), and any data will be similarly summarized. For participants with positive ADA or NAb, the magnitude (titer), time of onset, and duration of ADA or NAb response will also be described, if data permit.

The potential impact of immunogenicity on PK and clinical response including pharmacodynamic markers, safety/tolerability and efficacy will be explored, if warranted by the data. This analysis may be reported separately from the CSR.

## **6.4. Exploratory Endpoints**

The following exploratory endpoints analyses may be performed. The results may be presented separately from the main CSR.

### **6.4.1. Biomarker Analysis**

Biomarker data including DNA, RNA, protein, metabolites, or defined cell types resulting from analyses of peripheral blood, and/or BM biospecimens will be assessed based on the Biomarker Set.

Exploratory biomarker endpoints will not be reported in CSR, but in a separate biomarker report.

### **6.4.2. Patient-Reported Outcomes**

The following PRO analyses will be performed to support the CSR development. All other PRO analyses described in the study protocol but are not included in this SAP will be described in detail in a separate PRO analysis plan.

Analysis of the PRO endpoints will be based on the PRO Analysis Set.

## **Completion Status**

The number and percentage of participants who completed these instruments at each time point will be summarized, as will the reasons for non-completion of these measures. An instrument is considered completed if at least one item was answered by the participant.

## **EORTC QLQ-C30**

This questionnaire contains 30 questions organized into 5 multi-item functional scales, 3 multi-item symptom scales, a global health/quality of life scale, and 6 single item symptom scales. For each of the 15 scales, the results will be summarized using descriptive statistics including mean, SD, 95% CI, median, minimum, maximum at each timepoint. This will be performed based on the observed values as well as change from baseline values.

## **EORTC QLQ-MY20**

This questionnaire contains 20 questions organized into 2 functional scales and 2 symptom scales. As with QLQ-C30, the analysis of the QLQ-MY20 scales will consist of descriptive statistics based on observed values and change from baseline values.

## **6.5. Subset Analyses**

All the subset analyses will be exploratory; no adjustment for multiplicity will be performed. Analyses will only be performed if there is sufficient sample size. The determination of whether or not there is sufficient sample size will be defined after enrollment is complete and prior to database lock. As a general rule, analyses of ORR will only be performed if there are  $\geq 10$  participants overall within the defined subset. Deviations from these analyses will be described in the clinical study report.

The following subset analyses will be performed for ORR as determined by investigator for Phase 2 part only based on the Safety Analysis Set:

- Baseline cytogenetics (high vs standard risk);
- Baseline extramedullary disease (yes vs no);
- Disease stage (1-2 vs 3);
- Number of prior therapies ( $\leq 4$ ,  $>4$ );
- Type of myeloma (IgG vs other);
- Age ( $<65$  vs  $\geq 65$ ;  $<75$  vs  $\geq 75$ ).

ORR in subsets will be presented in a forest plot.

## **6.6. Baseline and Other Summaries and Analyses**

### **6.6.1. Baseline Summaries**

Analyses of baseline data will be based on the Safety Analysis Set.

#### **6.6.1.1. Demographic Characteristics**

The following demographic and baseline characteristics will be summarized by number and percentage:

- Gender (male, female);
- Age (18 to <65; 65 to <75; ≥75);
- Race (White, Black or African American, Asian, American Indian or Alaska Native, Native Hawaiian or other Pacific Islander, Not Reported, Unknown);
- Ethnicity (Hispanic, Not Hispanic, Not reported);
- Geographic Region (North America, Europe, Asia, Other).

Age (continuous), height (cm), weight (kg), BMI (kg/m^2) will be summarized with descriptive statistics (mean, median, standard deviation, minimum, and maximum).

#### **6.6.1.2. Medical History**

Medical history will be coded using the most current version of MedDRA and summarized by MedDRA's SOC and PT from the 'Medical History' CRF page. Each participant will be counted only once within each PT or SOC. Summaries will be ordered by SOC and PT in descending order of overall frequency in Phase 2. In case of equal frequency, alphabetical order will be used. Separate summaries will be provided for past and present conditions.

#### **6.6.1.3. Disease Characteristics**

The following baseline disease characteristics will be summarized by number and percentage:

- Primary diagnosis;
- Current disease stage by Revised Multiple Myeloma International Staging System (R-ISS, Stage I, II, and III, or unknown);
- Eastern Cooperative Oncology Group (ECOG) Performance status (0, 1);
- Cytogenetics (including high vs standard risk);
- Presence of extramedullary disease;
- Type of myeloma (IgG vs non-IgG or unknown);

- Type of Measurable disease at baseline (see [Section 5.2.9](#)):
  - Serum M-protein;
  - Urine M-protein;
  - Serum free light chain.

The following baseline disease characteristics will be summarized by descriptive statistics (mean, median, standard deviation, minimum, and maximum):

- Time since first diagnosis (months), defined as (date of first dose of study intervention – date of first diagnosis) / 30.4375;
- Time since onset of current episode, defined as (date of first dose of study intervention – date of onset of current episode) / 30.4375.

#### **6.6.1.4. Prior Anticancer Therapy**

The prior anticancer therapies are collected under the ‘Response to Regimen -Prior Cancer Therapy’, ‘Non-drug Treatments – Prior Radiation Therapy’ and ‘Transplant Details - Prior’ eCRF pages.

The number and percentage of participants in each of the following anticancer therapy categories will be tabulated:

- Participants with at least 1 type of prior anticancer treatment;
- Participants with at least 1 prior anticancer drug therapy;
- Participants with at least 1 prior anticancer radiotherapy;
- Participants with prior IMiDs and type (eg, lenalidomide, pomalidomide, or thalidomide);
- Participants with prior proteasome inhibitor and type (bortezomib, carfilzomib, ixazomib);
- Participants with prior anti-CD38 antibody and type (daratumumab, isatuximab);
- Participants who are Triple-class refractory (refractory to at least 1 of each type above);
- Participants with prior transplant and type (autologous or allogeneic);
- Prior anticancer drug therapy will be summarized as follows based on the number and percentage of participants;

- Number of prior anticancer therapy regimens: missing 1/2/3/4/≤4/>4;
- Best overall response on the last prior anticancer therapy regimen received;
- Reason for stopping the last prior therapy.

The prior anticancer drugs will be coded in the WHO Drug coding dictionary and will be summarized based on the number and percentage of participants by preferred term. A participant will be counted only once within a given preferred term, even if he or she received the same medication at different times. The summary will be sorted in descending order of the overall frequency of Phase 2. In case of equal frequency, alphabetical order will be used.

## 6.6.2. Study Conduct and Participant Disposition

### 6.6.2.1. Disposition

The percentages below will be calculated based on the number of participants in the Safety Analysis Set and summarized as follows:

- Number of participants enrolled and treated by country and site;
- Number and percentage of participants in each of the analysis sets defined in [Section 4](#);
- Number and percentage of enrolled participants with study intervention ongoing, discontinued or not given;
- Number and percentage of enrolled participants who discontinued the study intervention, overall and by the main reason for discontinuation of study intervention;
  - Discontinued PF-06863135;
  - Discontinued the combination partner agent (presenting the study drug name in the summary table).
- Number and percentage of participants who entered follow-up;
- Number and percentage of participants who discontinued follow-up, overall and by the main reason for discontinuation of follow-up;
- Number and percent of participants on Dose levels 1 and 2 escalated to the next higher dose level(s) (Phase 1b only).

In addition, dispositions related to COVID-19 may be presented in a separate listing if there is significant impact of COVID-19.

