## 4. ANALYSIS SETS (POPULATIONS FOR ANALYSIS)

For purposes of analysis, the following analysis sets are defined:

Participant Analysis Set	Description
DLT-Evaluable Analysis Set	
The DLT-evaluable analysis set will include all enrolled participants who receive at least 1 dose of the study intervention in the Phase 1b part of the study and either experience DLT(s) or complete the DLT observation period without DLT. Participants without DLTs who receive less than the minimum requirement of the planned doses of each IP for reason other than treatment-related toxicity are not evaluable for DLTs.
 
The DLT observation period is 35 days from Cycle 0 Day 1 through Cycle 1 Day 28.

090177e196913362\Approved\Approved On: 19-Mar-2021 12:41 (GMT)

	
The minimum required exposure for DLT evaluability is defined as follows:
 
 
• For PF-06863135 (all sub-studies): 4 out of 5 planned doses during the DLT observation period. Participants must be able to receive the full dose on Cycle 1 Day 1 (-1/+3 dosing window) and not require any dose reductions during the DLT observation period;
 
• For nirogacestat (sub-study A): at least 75% of the planned doses and not require any dose reductions during the DLT observation period.
 

Safety Analysis Set	The safety analysis set will include all enrolled participants who received at least 1 dose of study intervention.
PK Analysis Set	
The PK analysis set will include all participants in the safety analysis set who have at least 1 post-dose concentration measurement.
 
The PK parameter analysis set will include all participants in the safety analysis set who have at least one of the PK parameters of interest for PF-06863135.

Immunogenicity Analysis Set	The immunogenicity analysis set will include all participants in the safety analysis set who have at least 1 sample tested for ADA.
Biomarker Analysis Set	
The biomarker analysis set will include all participants in the safety analysis set who have at least 1 baseline biomarker assessment.
 
Analysis sets will be defined separately for biomarkers based on blood, and bone marrow samples.

PRO Analysis Set	The PRO analysis set will include all participants in the safety analysis set who completed a baseline (last PRO assessment prior to or on the first dose of study intervention) and at least 1 post-baseline PRO assessment.

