*Note:* "Enrolled" means a participant who is assigned to study intervention in IRT.

090177e196913362\Approved\Approved On: 19-Mar-2021 12:41 (GMT)

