**Phase 2 Design:**

Phase 2 will begin once the combination RP2D from the Phase 1b is selected. Approximately 50 participants will be enrolled in the Phase 2 part to assess anti-tumor activity and safety of elranatamab in combination with nirogacestat.

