### 6.6.2. Study Conduct and Participant Disposition

See [Section 6.5.2 of the master SAP](#) for summaries of study conduct and participant disposition.

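### Master SAP disposition table: the row that counts enrolled participants never given study intervention is expressed as a percentage of dosed participants only

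*SAP*

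**What the plan says.** Section 6.6.2.1 (Disposition) of the supplied master SAP, dated 18 March 2021, opens with a single rule for the whole table: "The percentages below will be calculated based on the number of participants in the Safety Analysis Set". Two of the rows beneath it are worded in terms of enrolled participants:

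- The row on treatment status reads: "Number and percentage of enrolled participants with study intervention ongoing, discontinued or not given".
- The next row, on stopping treatment, begins: "Number and percentage of enrolled participants who discontinued the study intervention, overall and by the main reason". It is then split by study drug.

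Section 4 of the same document supplies the definitions. "The safety analysis set will include all enrolled participants who received at least 1 dose of study intervention". A note under the table of analysis sets says that enrolled "means a participant who is assigned to study intervention in IRT". Section 4 defines no analysis set made up of everyone enrolled, and Section 6.6.2.1 makes no exception to its denominator rule.

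The sub-study A and sub-study B SAPs contain no disposition text of their own. Section 6.6.2 of each sends the reader to "Section 6.5.2 of the master SAP".

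**The concern.** Enrolment requires an IRT assignment; membership of the Safety Analysis Set also requires a dose. A participant who was assigned but never dosed belongs in the not-given category of the first row and cannot belong to the denominator used for it. A programmer following the text has two options. One is to count such participants in the numerator, so that three mutually exclusive states total more than 100%. The other is to restrict the numerator to the denominator, so that not given is zero whatever happened.

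The situation is foreseeable. Under the temporary enrolment hold in Section 7.2.1 of the master SAP and of both sub-study SAPs, someone newly enrolled may not begin treatment while the hold lasts. ORR and the safety summaries use the Safety Analysis Set, so disposition is the natural place for a reader to look for loss between assignment and first dose. What is at stake is whether the percentages there can be read at face value.

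**Working it through.** No figure in the plan depends on this row, so there is nothing to reproduce. The check is arithmetic on the plan's own definitions.

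**Inputs**

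- t = number dosed = size of the Safety Analysis Set (master SAP Section 4).
- u = number assigned in IRT but never dosed. The documents do not give this; values of 1, 3 and 5 are assumed.
- E = t + u = number enrolled (master SAP Section 4, note).
- Scale for illustration: the sub-study A SAP, Section 2.3, states "Approximately 50 participants will be enrolled in the Phase 2 part".

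**Formulas**

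- Stated denominator, untreated counted: sum of the three states = (t + u)/t; not given = u/t.
- Stated denominator, numerator restricted to dosed participants: sum = 100%; not given = 0/t = 0%.
- Enrolled denominator: sum = (t + u)/(t + u) = 100%; not given = u/(t + u).

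**Results with t = 50 dosed**

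| u (assumed) | Sum, stated rule | Not given, stated rule | Not given, of enrolled |
|---|---|---|---|
| 1 | 51/50 = 102% | 1/50 = 2.0% | 1/51 = 2.0% |
| 3 | 53/50 = 106% | 3/50 = 6.0% | 3/53 = 5.7% |
| 5 | 55/50 = 110% | 5/50 = 10.0% | 5/55 = 9.1% |

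**Results with E = 50 enrolled instead**

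| u (assumed) | Sum, stated rule | Not given, stated rule | Not given, of enrolled |
|---|---|---|---|
| 1 | 50/49 = 102.0% | 1/49 = 2.0% | 1/50 = 2.0% |
| 3 | 50/47 = 106.4% | 3/47 = 6.4% | 3/50 = 6.0% |
| 5 | 50/45 = 111.1% | 5/45 = 11.1% | 5/50 = 10.0% |

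With u = 0, both denominators give the same answer and the defect has no effect.

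**Which rows must move together.** The discontinued count in the first row is the overall discontinued count in the second. Changing the denominator of the first row alone would give one count two percentages in adjacent rows. For an illustrative 40 discontinued with t = 50 and u = 3, these would be 40/53 = 75.5% and 40/50 = 80.0%.

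**The case against.** The strongest reply is that little is lost. The first line of the same table asks for numbers enrolled and treated by country and site, and the disputed row asks for a number as well as a percentage. A reader might infer that untreated participants vanish from the report. The documents do not support that, because the raw not-given count is requested whatever the denominator, and enrolled minus treated gives the same figure if the country and site line is reported as two counts. This part of the reply stands.

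Other readings also go too far:

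- **A single category above 100%.** Only the sum must pass 100%, and only when u is above zero. Not given alone would do so only if the never-dosed outnumbered the dosed. In the first table above, the error in that percentage is at most 10.0 − 9.1 = 0.9 points.
- **The analysis-set row is also wrong.** Every set in Section 4 consists of dosed participants. Reporting each as a share of those dosed, with the Safety Analysis Set as a 100% reference line, is coherent.
- **The defect is established for both sub-studies.** Their pointers cite master SAP Section 6.5.2, but in the supplied document Section 6.5 is Subset Analyses and disposition is Section 6.6.2. The offset recurs: both sub-study SAPs cite master Section 6.6 for safety, which is Section 6.7 here. Table 1 of the sub-study A SAP also lists the 18 March 2021 document as its own version 1. The master SAP they cite may be one that was not supplied.

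A further reply is that not given could mean a partner drug never started after an elranatamab priming dose, which would keep the participant in the denominator. The row refers to study intervention as a whole and to enrolled participants, and individual drugs appear only under the next row. The text as written does not carry that meaning, and it would need rewording if that was the intention.

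**Conclusion.** The inconsistency is real and follows from the supplied master SAP's own definitions. Taken literally, the rule yields percentages that sum to (t + u)/t, or a not-given percentage fixed at zero. The size depends entirely on u, which is assumed here: about 102% to 110% in total for 1 to 5 never dosed alongside 50 dosed, and no effect if everyone enrolled is dosed.

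It is a minor reporting defect in a descriptive table. A reader might take it to affect efficacy or dose finding, but ORR, the DLT rate, the futility rule and the enrolment holds do not use this table. The conclusion applies to the supplied master SAP. That the same wording governs sub-studies A and B is plausible but not shown.

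**What to change.** In master SAP Section 6.6.2.1, state that the number enrolled (assigned in IRT) is the denominator for both rows worded in terms of enrolled participants: treatment ongoing, discontinued or not given, and discontinuation overall and by main reason. Keep the Safety Analysis Set as the denominator for the remaining rows, including the analysis-set row. The three states then sum to 100% for any u, and the discontinued count carries one percentage.

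Correct the pointers in Section 6.6.2 of the sub-study A and B SAPs so that they name the disposition section of the master SAP in force. If that is a different version from the one supplied, check whether it has the same denominator sentence.

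The cost is one sentence in the master SAP and one cross-reference in each sub-study SAP. No new data are needed, since the assignments are already in IRT.
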